6.4.7. AUC on global score of ARSSQ

The computation of the AUC on global score of the questionnaire will be made for patients with non-missing value at D1 and at least another non-missing time point between D2 and D11. Otherwise, the AUC will be missing.

The AUC will be computed by the trapezoidal rule from D1 to D11 (Acute Phase).

If the value at D11 is missing, then it will be estimated by the value at the last non-missing time point before D11.

AXIODIS CRO 13/47

7. STUDY PATIENTS

7.1. Disposition of patients

Enrolled patients as well as included and randomised patients will be summarised using frequencies and percentages.

The number and percentage of patients who withdrew prematurely after inclusion, are lost to follow-up as well as the number of completers will be described by treatment group and overall. All withdrawn patients after their inclusion will be described regarding their main reason for withdrawal.

7.2. Protocol deviations

Protocol deviations will be discussed during the data review meeting and the status (minor or major) of these deviations will be validated in order to identify the patients to be excluded from the Per Protocol Set.

Major deviations are defined by:

- Non-compliance with the inclusion or exclusion criteria;
- No assessment of the primary efficacy criterion (ARSSQ) at D1, D5±1 and D8-1 during the treatment period;
- Intake of forbidden medication: saline irrigation;
- Intake of wrong treatment, i.e. wrong treatment given to the patient after randomization;
- A compliance to study product intake below 80% or greater than 120%;
- More than 23 intakes of Babykids nasal spray.

All other deviations will a priori be considered as minor, e.g.:

- V2's date that does not conform with the flow chart of the study;
- V2 not performed;
- Treatment stopped before D8 morning or after D11 morning (less than 14 intakes of the investigational device or more than 20 intakes);
- ARSSQ data missing (but data available at D1, D5±1 and D8-1) until patient's recovery (two consecutive and negative "not sick" answers to the first item) or D18/patient's end of study, whichever occurs first.

Major and minor deviations and their types will be described by treatment group and overall. They will be summarised with frequencies and percentages.

Patients will be counted only once within each type of deviation and within each category (major/minor).

A listing of all deviations will be provided for all included patients, including the category.

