9.2 Methods for data entry and collection

A validated electronic case report form (eCRF, 21 CFR Part 11 compliant) will be used to collect clinical data for this study. Some of the study data will be recorded in the paper diary by parents/legal guardians:

- Daily ARSSQ
- Adverse events/incidents
- Concomitant treatments

Investigators will validate adverse events pertinent in the context of the common cold, incidents linked to medical device use and concomitant medications reported in the paper diary. They will complete the e-CRF accordingly.

The sponsor is responsible for designing the e-CRF. eCRF training will be provided to appropriate personnel before/at initiation of the investigation site. Parents/legal guardians will be instructed how to complete the paper diary during visit V1.

9.3 Procedure used for eCRF tracking, data review, database cleaning and issuing/resolving data queries.

The Data Management process includes all activities related to data handling regarding:

- Set-up of eCRF and database
- Specification of on-line checks
- Data entry/Data editing
- Export of data from e-CRF to SAS database
- Creation of post-entry checks and listings
- Clean-file process including execution of post-entry checks and listings
- Post clean-file tasks

Data entry will be done by investigators and other authorized personnel at the sites. When entering data, on-line checks are encoded in the eCRF for consistency and validation. Whenever required, queries issued from this review will be submitted to the investigator for resolution and then tracked until corrections are entered and validated.

A data blind review meeting will be held prior to database lock.

The data review meeting prepared by the project manager, data manager, study monitor, medical manager and statistician will be attended by at least the following:

- Coordinating investigator,
- Study monitor,
- Sponsor Vigilance representative,
- Project managers from the sponsor and from the CRO,
- Data manager,
- Statistician.

The review is also required for defining the analysis populations and validating the statistical analysis plan.

The meeting will be documented by written and signed minutes that will act as the basis for data processing by the Biometrics Department.

All decisions on the evaluability of the data from each individual subject for the statistical analysis must be made and documented before locking the database.

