9.7 Procedure for data retention

Once the Clinical Investigation Report is signed and validated, the data are archived on a dedicated hard disk file with limited access rights. This specific file is mounted on AXIODIS's OVH server with a back-up every two months as well as copied to an external disk that will be stored under seal within the premises of AXIODIS. The data are conserved for at least 10 years.

Page 44 of 64

Version 1.1 –2023.02.02

Study Number: LPH-2202

10. Amendments to the CIP

Investigators should not implement any changes of the protocol without agreement by the sponsor.

All changes to the protocol are subject to an amendment which must be dated and signed by the sponsor and Principal Investigators and must appear as an amendment to the protocol.

Substantial amendments are notified to the EC and CA.

11. Deviation from Clinical Investigation Plan

A major protocol violation is a deviation that has an impact on subject safety, may substantially alter risks to subjects, may have an effect on the integrity of the study data, or may affect the subject's willingness to participate in the study. In this PMCF study, the following deviations are considered major:

- Non-compliance with the inclusion or exclusion criteria,
- No assessment of the primary efficacy criterion (ARSSQ) at D1, D5±1 and D8-1 during the treatment period,
- Intake of wrong treatment, i.e, wrong treatment given to the patient after randomization
- A compliance to study product intake below 80% or greater than 120%
- Intake of forbidden medication, i.e., nasal irrigation

All other cases will, a priori, be considered as minor deviations.

All protocol deviations will be managed as per the Standard Operating Procedures of the CRO.

A deviation log shall be maintained by the study site.

All deviations will be included, as required in the final study report.

Any major deviation from the protocol that has not been previously approved by the sponsor must be reported to the sponsor within 2 working days of the deviation occurrence. Any deviations from the clinical investigation plan that are identified during routine monitoring visits will be reported to the sponsor within 24 hours of being identified.

In case of major deviation, corrective and preventive actions will be implemented as per Study Deviation Management plan and Risk management plan.

12. Device accountability

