5. DEFINITION OF THE ANALYSIS SETS

Enrolled patients: all patients whose parents/legal guardians signed an informed consent.

Included patients: all the enrolled patients who participated in the study.

Randomised patients: all the included patients who were assigned a treatment number.

Safety population: all the randomised patients who used the nasal spray at least once.

Full Analysis Set (FAS): all the patients from the Safety population and with at least one postbaseline efficacy data.

Any patient not satisfying major entry criteria or for whom post randomisation data are not available will be identified by the Validation Committee during the data review, and could be excluded from the FAS in agreement with circumstances exposed in the ICH-E9 §5.2.1.

Per Protocol (PP) Set: Efficacy population based on the FAS without patients with major protocol deviations.

The status of protocol deviations (minor or major) will be validated during the data review meeting.

Safety endpoint will be performed on the Safety Set.

The analyses of primary and secondary endpoints will be performed on the FAS.

The primary and one secondary (modelling of AUC on global ARSSQ score by multivariate ANCOVA) endpoints will also be analysed on the PP set, analyses on the PP set being supportive in superiority trials.

AXIODIS CRO 9/47

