9. COMPLIANCE

Compliance will be calculated according to the following formula and analysed on the Safety set, by treatment group and overall.

The compliance will be calculated as follows:

Compliance (%) = [Initial weight of the container (g) – Real weight of the container at the end of the study (g)] \times 100 / [Initial weight of the container (g) – Theoretical weight of the container at the end of complete study (g)]

with:

- Initial weight of the container = 32.615 g;
- Theoretical weight of the container at the end of complete study is a function of treatment duration and is noted *weight*_{theo};

i.e.:

Compliance (%) =
$$100 \times \frac{32.615 - weight_{end}}{32.615 - weight_{theo}}$$

with weightend the real weight of the container at the end of the study in g.

The table below gives the value of $weight_{theo}$ by last day of treatment:

Table 1: Theoretical weight of the container at the end of complete study by last day of treatment

Patient stopped treatment	weighttheo (g)
Before D8	27.55875
At D8 morning	27.55875
At D8 evening	27.21750
At D9 morning	26.85750
At D9 evening	26.53750
At D10 morning	26.21500
At D10 evening	25.87125
At D11 morning	25.52500
At D11 evening	25.20250
At D12 morning	24.86500
At D12 evening	24.51000
After D12	24.51000

Compliance will be also described according to the following categories: <80%, [80%; 120%] and >120%.

Note that in case of spray not returned, compliance will be considered unknown and missing.

AXIODIS CRO 16/47

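### SAP 7.2 words the over-exposure major deviation for the active product only, so Per Protocol membership is defined differently by arm and the rule cannot be applied at the blind data review

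*SAP*

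**What the plan says.** SAP 5 defines the PP Set as "Efficacy population based on the FAS without patients with major protocol deviations", so the list of major deviations in SAP 7.2 decides who is in it. Three rules in that section bear on over-use:

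- **Major, one product named:** "More than 23 intakes of Babykids nasal spray".
- **Major, arm-neutral:** compliance outside 80 to 120%, also in protocol section 11 ("A compliance to study product intake below 80% or greater than 120" per cent).
- **Minor, arm-neutral:** "Treatment stopped before D8 morning or after D11 morning (less than 14 intakes of the investigational device or more than 20 intakes". The protocol synopsis uses the same device term when it describes the placebo arm.

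For anything not listed as major, SAP 7.2 says "All other deviations will a priori be considered as minor".

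Compliance is obtained by weighing the bottle. SAP 9 divides the weight used by an expected weight that depends on the stop day (Table 1, "Theoretical weight of the container at the end of complete study by last day of treatment"). D12 evening and any later stop share one value. If the spray is not returned, compliance is set to missing.

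SAP 7.2 has the data review meeting settle deviations: "the status (minor or major) of these deviations will be validated in order to identify the patients to be excluded from the Per Protocol Set". Protocol 9.3 says "A data blind review meeting will be held prior to database lock" and requires evaluability decisions to be documented before lock. Protocol 7.1.2 places unblinding after lock.

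Protocol section 11 has no intake-count rule, and SAP 12 does not list one as a change.

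**The concern.** An exclusion rule that depends on the treatment received undoes, within the PP Set, the comparability that randomisation provides. Two children with the same exposure would be classified differently because of their arm.

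The wording also conflicts with the process around it. Those who fix the PP Set before lock do not know who received Babykids. They can apply the count to every child, which departs from the text, or hold the rule back until the code is broken, which departs from the blind-review plan. The SAP does not say which.

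The PP runs of the primary AUC comparison (SAP 10.1) and of the ANCOVA (SAP 10.2.1) are at stake. If the rule were applied by arm and the excluded children had above-average AUC, the active mean would fall in the PP Set with no matching change in placebo.

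**Working it through.** **1. Intakes to days.** Protocol 7.4.1 puts the first use on D1 evening, then two per day.
- D8 morning: 1 + 2×6 + 1 = 14. D11 morning: 1 + 2×9 + 1 = 20. Both reproduce the plan's own 14 and 20.
- D12 evening: 1 + 2×11 = 23. Intake 24 therefore falls on D13 morning.

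**2. When the arm-neutral 120% rule catches a placebo child.** Initial weight is 32.615 g (SAP 9). For a stop at D12 evening or later, the denominator is 32.615 − 24.510 = 8.105 g, or 8.105/23 = 0.352 g per intake. At that rate, compliance = 100 × intakes/23:

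| Intakes | 24 | 25 | 26 | 27 | 28 |
|---|---|---|---|---|---|
| Compliance | 104% | 109% | 113% | 117% | 122% |

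The limit is 1.20 × 23 = 27.6, so 28 intakes are needed.

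**3. Dependence on stop day.** More than 23 intakes can also come from extra daily use with an earlier stop. At each Table 1 row's own average delivery:

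| Last intake | Planned intakes | 120% limit | First count above 120% | Counts treated differently by arm |
|---|---|---|---|---|
| D11 morning | 20 | 24.0 | 25 (125%) | 24 |
| D11 evening | 21 | 25.2 | 26 | 24–25 |
| D12 morning | 22 | 26.4 | 27 | 24–26 |
| D12 evening or later | 23 | 27.6 | 28 (122%) | 24–27 |

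**4. Dependence on delivery (stop at D12 evening or later).** At 0.361 g per intake (the D8-morning row: 5.05625/14), 27 intakes give 120.3%. At an assumed 0.34 g, 29 are needed (121.7%). The pump is specified at 100 ± 20 µl (protocol 3.7.1). If a bottle delivered 20% above the Table 1 average throughout, 24 intakes would already give 24 × 1.2/23 = 125%. An unreturned bottle has no compliance value, so no upper limit applies.

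**5. Size if the rule were applied to the active arm only.** Let f be the share of the active arm removed and d the excess of their mean AUC over the arm mean, in SD. The PP difference then shifts by f·d/(1 − f). With 100 per arm, SE = √(1/[100(1 − f)] + 1/100). The documents give neither f nor d, so these are assumed ranges, with d from 0.5 to 1.5:

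| f | Shift (SD) | Two-sided rejection rate under the null |
|---|---|---|
| 1% | 0.005–0.015 | 0.050–0.051 |
| 2% | 0.010–0.031 | 0.051–0.055 |
| 5% | 0.026–0.079 | 0.054–0.085 |
| 10% | 0.056–0.167 | 0.067–0.209 |

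**6. Same limit in both arms.** With similar over-users in each arm and no treatment effect, the differential shift is 0. The planned 100 per arm gives power 0.807 at an effect size of 0.4 (normal approximation; 0.804 by the exact t-test), consistent with the plan's 80%. Removing 1, 2, 5 or 10% from each arm leaves PP power at 0.804, 0.800, 0.787 or 0.765.

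**The case against.** **One-arm removal is not what the process would produce.** A reader might infer that the rule removes active children while leaving placebo children in. The documents do not support that as an outcome. Under the blind pre-lock review, an intake count can be applied only to everyone or to no one, and removal by arm would need a departure from that process. This stands: selection bias is not established. The wording still contradicts the process that has to use it.

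**Babykids may be shorthand for the study spray.** The trial acronym is built on the name, and the protocol is loose elsewhere: it refers to a Healsea Placebo and mixes terms when describing the placebo arm. This is plausible, but no text says so, and the rules alongside use neutral terms.

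**Over-users need not be the sicker children.** A reader might infer that children beyond 23 intakes are still ill, so that the bias must favour the device. There is partial support: before D11 a child should stop only after being rated not sick on two consecutive days, so those treated to D11 are expected to be mainly the slower recoverers. But the schedule ends by D11 morning whatever the symptoms, so going past 23 intakes shows overrun. On regular dosing, intake 24 also falls after the D1–D11 AUC window. The direction is an inference.

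**The 120% rule covers part of the gap.** This is correct, as steps 3 and 4 show. The range of 24 to 27 intakes holds only for a stop at D12 evening or later at Table 1's average delivery.

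**Little depends on it.** SAP 5 calls the PP analyses supportive, and SAP 6.3.1 confines conclusions to the primary criterion, which is analysed on the FAS. Deviations are also tabulated by arm and listed with PP status (mock tables T2 and L1), so any imbalance would be visible. This stands and sets the severity.

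**Conclusion.** The rule is wrong as written, at minor severity. Its text makes PP membership depend on treatment arm, it cannot be applied as worded at the blind review, and it is an undisclosed addition to protocol section 11.

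The difference between arms is narrow: one to four intake counts, depending on stop day, plus unreturned bottles. This assumes Table 1's average delivery. Any bias requires the rule to be applied by arm after unblinding, and it favours the device only if over-users have higher AUC. With 1 to 2% of the active arm removed, the assumed range gives 0.005 to 0.031 SD and a null rejection rate of at most 0.055. The larger scenarios rest on over-use shares that nothing in the documents supports. The effect is probably small, and the FAS conclusion is unaffected.

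**What to change.** - In SAP 7.2, word the intake-count deviation identically for the study nasal spray in both arms.
- State that it is applied blind at the data review meeting, before lock.
- List it in SAP 12 as an addition to the major deviations in protocol section 11, so that the two lists are reconciled.

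No view is taken on which intake limit is right. The cost is one line in SAP 7.2 and one entry in SAP 12. No new data are needed, and the FAS analyses do not change.

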7.3. Data Sets Analysed

The number and percentage of patients in each analysis data set, as described in §5, will be provided.

AXIODIS CRO 14/47

Statistical Analysis Plan

8. Demographic and other baseline characteristics

All demographic and baseline characteristics will be described on the Safety Set and on the FAS, by treatment group and overall.

BASICC

8.1. Demographic characteristics

Age (years) and sex will be summarised using descriptive statistics already mentioned in §6.2. Age will be computed using the formula below:

Age (years) = Collected Age (years) + [Age precision in months] / 12 (rounded at 1 digit)

8.2. Previous medications

Previous and concomitant medications (taken at least once before reference start date) are coded by ATC class and substance name using the WHO-DRUG dictionary version 2022 Q1.

They will be summarised with frequencies and percentages.

Patients will be counted only once within these ATC categories.

Moreover, answers to questions about past or concomitant forbidden medications and about concomitant treatments for first symptoms of infectious rhinitis will be summarised.

8.3. Medical and surgical past history

Medical and surgical past history is coded using the MedDRA dictionary version 25.0. Events are classified by System Organ Class and Preferred Term.

The number and percentage of patients with at least one medical and surgical past history of each category (SOC/PT) will be given.

Patients will be counted only once within these categories.

8.4. Acute Rhinitis Symptoms Severity Questionnaire

The scores to each of the ten items of the ARSSQ, the score of cold symptoms (the sum of the scores to the items 2 to 7), the score of impact on Quality-of-Life (the sum of the scores to the items 8 to 10) and the global score (the sum of the scores to all the ten items) will be described at baseline.

A Student (or Wilcoxon if the normality assumption is not acceptable) between-groups test will be performed for each score.

8.5. Other baseline variables

The presence of fever in the patient and the reported body temperature will be summarised. The presence of fever in each group will be compared by means of chi-square or exact Fisher test.

A Student (or Wilcoxon if the normality assumption is not acceptable) between-groups test will be performed for the reported body temperature.

AXIODIS CRO 15/47

9. COMPLIANCE

Compliance will be calculated according to the following formula and analysed on the Safety set, by treatment group and overall.

The compliance will be calculated as follows:

Compliance (%) = [Initial weight of the container (g) – Real weight of the container at the end of the study (g)] \times 100 / [Initial weight of the container (g) – Theoretical weight of the container at the end of complete study (g)]

with:

- Initial weight of the container = 32.615 g;
- Theoretical weight of the container at the end of complete study is a function of treatment duration and is noted *weight*_{theo};

i.e.:

Compliance (%) =
$$100 \times \frac{32.615 - weight_{end}}{32.615 - weight_{theo}}$$

with weightend the real weight of the container at the end of the study in g.

The table below gives the value of $weight_{theo}$ by last day of treatment:

Table 1: Theoretical weight of the container at the end of complete study by last day of treatment

Patient stopped treatment	weighttheo (g)
Before D8	27.55875
At D8 morning	27.55875
At D8 evening	27.21750
At D9 morning	26.85750
At D9 evening	26.53750
At D10 morning	26.21500
At D10 evening	25.87125
At D11 morning	25.52500
At D11 evening	25.20250
At D12 morning	24.86500
At D12 evening	24.51000
After D12	24.51000

Compliance will be also described according to the following categories: <80%, [80%; 120%] and >120%.

Note that in case of spray not returned, compliance will be considered unknown and missing.

AXIODIS CRO 16/47

10. EFFICACY

10.1. Analysis of the primary efficacy criterion

The primary objective will be analysed by performing a t-test (or a Wilcoxon test if the normality assumption is not acceptable) on the means of AUC on global score of ARSSQ during the first eleven days of the study between treatment groups.

The answers of the ten items of ARSSQ are scored from 0 to 3 (0: negative answer; from 1 to 3: positive answer with an increasing severity level). See the daily report in appendix (§13.3). The global ARSSQ score at each time point is the sum of the scores to the ten items of the ARSSQ:

At each time point t: ARSSQTOT(t) =
$$\sum_{j \text{ in } \{1; ...; 10\}} ARSSQ_j(t)$$

AUC of global ARSSQ score will be computed by the method described in §6.4.7.

Patients will be analysed on the FAS and the PP Set. In each case, boxplots of the AUC on global score will be realized by treatment group. The number of available data and the p-value will be printed on the figure.

